2.4. Primary analysis/results

Purpose: Primary results for the intention to treat (ITT) analysis.

Methods/Approach:

Intention to Treat Dataset: all subjects randomized into study and all data observed from each subject regardless of compliance and adherence with the assigned intervention or follow-up.

Primary outcome: Change in systolic BP from baseline (median of three qualifying SBP from eligibility phase) to 12 months. Baseline minus 12 months.

Primary analysis: The primary analysis will fit a linear regression model with the outcome of SBP change and main effect-coded binary predictors of healthy behavior texts (yes vs. no), prompted BP self-monitoring frequency (high vs. low), and primary care provider visit scheduling and transportation (active vs. passive) and the stratification variables. Initial analyses will focus on the main effects. The outcome will be transformed (e.g., log) if necessary.

$$(BL\ BP - 12\ mo\ BP) = \beta_0 + \beta_1\ HBtexts + \beta_2\ HighBPmonitor + \beta_3\ PCPfacilitated + \beta_4\ female + \beta_5\ Age > 65 + \beta_6\ AHT + \beta_7\ Black$$

Where HBtexts= 1 for daily healthy behavior texts and 0 for none; HighBPmonitor=1 if daily BP monitoring and 0 for weekly; PCPfacilitated=1 for provider scheduling and transportation facilitated and 0 for not facilitated; female = 1 for self-reported female, 0 for male; Age>65=1 for Age \geq 65, 0 for 18-64; and AHT=1 for antihypertensives in the past 6 months, 0 for not; Black=1 for Black, 0 for Other

Missing data:

We will work to prevent missing data by the recruitment and retention strategies described elsewhere. The amount and patterns of missing data and its associations with other variables (in particular intervention category) will be explored so that an appropriate statistical method for analysis can be used. If the data is missing at random (missing outcomes can be predicted from other observed variables, especially recent self-reported blood pressures), which we believe to be the most likely, since we obtain text messaging-based BPs at least weekly, the repeated measurements within individuals will allow us to use multiple imputation to handle sporadic missing at random BP measurements. For multiple imputation, we will use R package mice to impute the data using multiple imputation by chained equations. Non-normal continuous missing variables will be transformed for normality and back-transformed for any calculations necessary (e.g., change in BP). The imputation model will include all variables in the analysis model, treatment interactions, as well as other covariates that predict the missing variable and whether the missing variable is missing. Thus, associations between baseline variables and missing variables will be assessed both for strength of association and functional form. We will use 100*fraction of incomplete cases number of imputations. Analyses will combine regression estimates using Rubin's rules. Model checking will be performed on each imputed dataset through residual analysis to identify any issues with the imputation model or analysis model. Problems occurring in a small number of imputed datasets suggest a problem with the imputation dataset and problems occurring consistently across all imputed datasets suggest a problem with the analysis model.

In the case of non-ignorable missing (missing not at random) data, sensitivity analyses will be performed using pattern mixture or selection models to evaluate the robustness of our conclusions to a range of sensible conditions (for both the primary and additional analyses of the primary endpoint).

Interpretation:

Results will be reported as parameter estimates, 95% confidence intervals, and 2-sided p-values. As the goal of this exploratory trial is to find interventions and combinations with activity, we will use an alpha level of 0.10 for all main effects. Plots of mean BP levels over time will be generated for the 3 main effects and each intervention group.

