1.1 Primary Endpoint

Reduction in systolic BP from baseline (median of three qualifying SBP from eligibility phase) to 12 months.

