5.3.4 Eligibility phase

Following consent, because some participants will have isolated hypertension in the ED, participants will undergo a 3-week eligibility phase (beginning after informed consent, and participant has received blood pressure cuff) to determine if they have persistently elevated BP. All participants enrolled in the study will be given an automated BP cuff, American Heart Association or American College of Cardiology information about high blood pressure (Appendix B), and receive a text message one day in a week asking to text in their own BP. If a participant has not responded by the end of week 2 of the eligibility phase, a study team member may contact up to 2 times to assure it is not a technical issue. This is based on feedback from our previous studies, where participant's primary reported reason for unresponsiveness was unaddressed technical complications.

If participants have 1) persistent high blood pressure (any self-reported BP (SBP) \geq 140 or a BP (DBP) \geq 90), and 2) responded to texts at least once, they will be randomized into the trial. If participants do not meet both criteria, they will receive no further communication from the study team following the eligibility phase. These participants may be texted a final text message thanking them for participation.

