Incentive	X											X						X	
Cognitive screen	X																		
ED Measured BPs	X																		
Competence w/BP cuff	X					X													
Competence with text messaging	X					X													
ASSESSMENTS:																			
Contact Information	X											X						X	
Demographics	X																		
Medical History	X																		
Tobacco/ Alcohol	X																		
Insurance Status	X																		
Transportation	X																		
SCT measures	X											X						X	
Self- efficacy modified						X	X	X	X	X		X	X	X	X	X	X		
SCT modified	X											X						X	
Self- reported BP measurement		X	X	X															
Study taken BP measurement	X											X						X	
PCP:																			
PCP	X											X						X	
First PCP visit time												X						X	
PCP attendance	X					X	X	X	X	X	X	X	X	X	X	X	X	X	

Reach Out ED
Version 14.0
1 August 2022

BP medication adherence will be assessed using several different methods: 1) Hill-Bone and one-question modified Hill-Bone question; 2) pharmacy and provider notes; 3) text participants to message pictures of their medication prior to the 6 and 12 month follow-ups. We will also ask participants to bring their medication to the 6 and 12 month follow-ups. For participants that have not done either, they will be reminded at the follow-up appointments, and texted once more afterwards. In an attempt to further monitor medication adherence, we will look for medication fill rates within the Hurley EHR, and Hamilton pharmacy records, and if there are linkages to commercial pharmacy, we will scan electronic record to assess. We will evaluate the impact of the interventions, and a brief survey regarding participant feedback on the specific intervention components they received (will be added in a future amendment).

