2.6 Subgroup analyses

Purpose: To evaluate the heterogeneity of treatment effects by baseline characteristics of age, sex, previous antihypertensive medication, race, and baseline BP level.

Methods/Approach:

- To assess the heterogeneity of treatment effects by age, sex, previous antihypertensive medication and race, the two-way interactions of the main effects of treatments and these covariates will be assessed at the 0.2 significance level
- To assess the heterogeneity of treatment effects by baseline BP, we will divide the cohort into tertiles based on their initial BP level (median of three qualifying SBP from eligibility phase). We will repeat the above primary (Section 2.4) and secondary modeling (Section 2.5a) within each of the three initial BP strata to determine if there is heterogeneity of effect (e.g. do patients with the highest baseline BPs get the most benefit from the intervention components?).

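### Baseline SBP is defined as a median of three readings, but one reply is enough to be randomized, and the primary model leaves baseline SBP out

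*SAP*

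**What the plan says.** - **Definition.** Protocol 1.1 gives the primary endpoint as "Reduction in systolic BP from baseline (median of three qualifying SBP from eligibility phase) to 12 months". SAP 2.4 repeats that baseline in its primary outcome, "Change in systolic BP from baseline (median of three qualifying SBP from eligibility phase) to 12 months", and SAP 2.6 uses it to cut the cohort into tertiles.
- **Collection.** In protocol 5.3.4 the eligibility phase lasts three weeks, and enrolled participants "receive a text message one day in a week asking to text in their own BP". The schedule of measures after protocol 7.2 marks "Self- reported BP measurement" in three screening columns.
- **Entry.** Protocol 5.3.4 requires any one self-reported SBP >=140 or DBP >=90 and at least one reply: people who "responded to texts at least once, they will be randomized into the trial". A participant who "has not responded by the end of week 2 of the eligibility phase" may be contacted, so late responders are expected.
- **Analysis set.** SAP 2.4 takes everyone randomized and plans multiple imputation of sporadic missing BPs, with change calculated afterwards. Its regression adjusts for sex, age group, antihypertensive use and race, but not for baseline SBP.
- **Another baseline reading.** Protocol 7.1.1 says the research team measures BP at baseline, and the schedule marks "Study taken BP measurement" there.

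**The concern.** The definition needs three readings and the entry rule needs one. Anyone randomized on one or two replies is in the analysis set with no baseline as written, and so no primary outcome as written. The plan leaves open whether to use the readings that exist, impute the missing reading, impute the whole baseline, or drop the person.

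*Qualifying* adds a second ambiguity: it could mean every reading from the eligibility phase, or only readings that met a threshold. At stake are an unspecified step in the primary outcome, the membership of the baseline tertiles, and the average level of change. That level matters because, in a null trial, SAP 1 and protocol 9.1 test the arm 1 intercept against zero at p=0.1 to choose the next study.

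**Working it through.** No figure stated in the plan is in dispute. The check sets the rules side by side and then sizes the consequences under stated assumptions.

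**1. Readings available.** 3 weeks x 1 prompt a week = 3 planned readings, so a median of three needs a reply to every prompt. Someone silent for two weeks has 3 - 2 = 1 prompt left and cannot reach three prompted readings.

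**2. Does the imputation text settle it?** No. It does not say whether the missing reading or the whole baseline is imputed, and the second would set observed readings aside. The number of imputations is 100 times the fraction of incomplete cases. That fraction cannot be computed until someone decides whether a person with two readings is incomplete.

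**3. Effect on the component contrasts.** Any baseline formed from eligibility-phase readings has the same expected distribution at both levels of each factor. The expected difference in change therefore equals minus the difference in 12-month mean SBP, whichever rule is used.

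**4. Share affected (illustration only).** The documents give no response rate for the eligibility phase. The one rate for weekly prompts is the church pilot in protocol 2.2.1, 587/1248 = 47.0%, from six months in another setting. With response probability p per prompt, the share of responders without three readings is 1 - P(3 replies)/(1 - P(0 replies)).

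| p (assumed) | Independent replies | Within-person correlation 0.7 (beta-binomial) |
|---|---|---|
| 0.47 | 1 - 0.104/0.851 = 88% | 38% |
| 0.80 | 1 - 0.512/0.992 = 48% | 17% |
| 0.90 | 1 - 0.729/0.999 = 27% | 9% |

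These shares are of responders. Among the randomized they are lower, because three replies give more chances of one high reading. In the simulation in step 5, with independent replies, 44-47% of those randomized lacked three readings at p = 0.80, and 85-87% at p = 0.47.

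**5. Level of change with no true effect.** The simulation used 300,000 people per scenario and entry on any SBP >=140. Assumed values were population mean SBP 140-150, between-person SD 15-20, within-person SD 8-12 mm Hg and response 47-80%. Entry through diastolic BP was not simulated. Apparent mean 12-month reductions were:

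| Baseline used | Apparent reduction (mm Hg) |
|---|---|
| Median of all available readings | 0.5 to 3.6 |
| Median of readings >=140 only | 1.9 to 7.1 |
| People with one reading (all-readings rule) | 1.6 to 6.1 |
| People with three readings (all-readings rule) | 0.3 to 1.1 |

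For scale, protocol 9.3 takes 1 mm Hg as the minimal important effect of a component.

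**6. Precision from a baseline covariate.** Let r be the correlation of baseline with 12-month SBP and k the ratio of baseline SD to 12-month SD. Residual variance with the covariate, relative to the change score without it, is (1 - r²)/(k² + 1 - 2rk).

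| r (assumed) | k = 1 | k = 0.75 |
|---|---|---|
| 0.3 | 0.91/1.40 = 0.650 | 0.91/1.1125 = 0.818 |
| 0.5 | 0.75/1.00 = 0.750 | 0.75/0.8125 = 0.923 |
| 0.7 | 0.51/0.60 = 0.850 | 0.51/0.5125 = 0.995 |

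Residual variance falls by 15-35% with equal SDs. If selection at entry narrows the baseline SD to 0.75 of the 12-month SD, it falls by 0.5% to 18%.

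**The case against.** The best defence is that this is a one-line derivation rule and the SAP already points towards it. The analysis set takes all data observed from each person, which favours using the readings that exist. SAP 2.1 creates derived variables with the arms combined, so the choice could be made without sight of treatment effects. With three weekly prompts, the natural meaning of *qualifying* is simply the eligibility-phase readings. A change score without a baseline covariate is unbiased under randomization, so adding one is optional.

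Much of this stands. It narrows the likely intent and makes data-driven choice less of a worry, but it does not supply the rule. On the covariate, the lack of bias is granted; the argument is precision, from a value the trial already collects, and the gain may be negligible if r is high and k is low.

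A reader might go further in three ways that the documents do not support:

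- **The component effects are biased.** They are not, by step 3.
- **Upward selection of baseline arises only if *qualifying* means >=140.** It does not. A person with one reply enters only if that reply met the systolic or diastolic threshold, so one-reading baselines are selected under any definition. The narrower reading makes this worse.
- **A person who enters on diastolic BP alone has no usable baseline.** That follows only under the narrow reading, which is the less natural one.

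**Conclusion.** The point holds and should be fixed. The stated baseline cannot be computed for randomized participants with fewer than three readings, and neither document says what replaces it. This rests on the text alone. How many people are affected is unknown; the shares above depend on assumed response rates and on how replies cluster within people, and the pilot rate is not an estimate for this phase.

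The randomized main effects are protected. The outcome derivation, the tertiles and the arm 1 intercept are not. Under the assumed BP distributions, choosing between all readings and only those >=140 moves the apparent change by more than 1 mm Hg in most scenarios. The precision gain from the covariate runs from 35% down to under 1% of residual variance, on assumed correlations and SD ratios.

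**What to change.** 1. **Define baseline.** In protocol 1.1, SAP 2.4 and SAP 2.6, make it the median of all SBPs texted in the eligibility phase, whether or not >=140, with at least one required. Entry already requires a reported BP, so everyone randomized then has a baseline, and observed readings are used rather than imputed over.
2. **Adjust for it.** Add baseline SBP, centred at its mean, to the SAP 2.4 model, with matching text in SAP 1 and protocol 9.1. Centring keeps the intercept at the mean baseline instead of at an SBP of zero.
3. **Reconcile protocol 7.1.1 with the eligibility-phase definition.** State which reading is the endpoint baseline and what the other is for.
4. **State the remaining limit.** Regression to the mean stays in the arm 1 intercept under any definition, because the same readings select people for randomization.

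**Cost.** Wording edits in six places (protocol 1.1, 7.1.1 and 9.1; SAP 1, 2.4 and 2.6) and one covariate, with no new data. Baselines from fewer readings are noisier: for unselected normal readings, within-person error variance is 1.00 for one and 0.50 for two, against 0.45 for the median of three. One-reading baselines are also shifted upward by the entry threshold, so the number of replies still has some influence on tertile membership.

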9 STATISTICAL CONSIDERATIONS

9.1 Data analysis

The primary analysis (aim 1) will fit a linear regression model with the outcome of SBP change (baseline minus 12 months) and main effect-coded binary predictors of healthy behavior texts (yes vs. no), prompted BP self-monitoring frequency (high vs. low), and primary care provider visit scheduling and transportation (active vs. passive). Initial analyses will focus on the main effects. Additional analyses will include all the two-way interactions of the three intervention components (only considering interactions where at least one of the factors in the interaction demonstrates a sufficiently large main effect). As the goal of this exploratory trial is to find interventions and combinations with activity, we will use an alpha level of 0.10 for all main effects and 0.20 for interactions. We plan to include elements meeting that bar for statistical significance in the subsequent multicenter trial. If significant interactions exist (i.e. the combination of facilitated transportation and high frequency home BP monitoring), we plan to implement the combination of elements that has the highest expected reduction in SBP – assuming we achieve significance at the $p=0.1$ (main effects) or 0.2 (interaction) level for the components. In the event of an overall “null” trial, we would examine the expected change in SBP for arm 1, which would be represented by the intercept. If this was significantly greater than 0 at the $p=0.1$ level we would propose a very simple subsequent multi-center trial using only weekly prompted BP self-monitoring.

The main secondary analyses (aim 2) will use time-to event (Cox Proportional Hazards) and logistic regression. For the endpoint of interest, (either time to first primary care visit, or the binary variable indicating attendance at two or more primary care visits within 1 year of randomization), we will fit an adjusted regression model. The main predictor of interest for these models is assignment to the active primary care provider scheduling and transportation arm (50% of all

participants randomized in the trial), while adjusting for the assignment into other groups similar to aim 1 (healthy behavior text messages and prompted BP self-monitoring).

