We will conduct additional exploratory analyses using the stratification factors (age, sex, and antihypertensive use) as covariates. As uncertainty exists on the distribution of enrolled participants within these strata (e.g. young men taking antihypertensive medication), we cannot estimate the preliminary statistical power for these exploratory aims. Thus, we will estimate the power based on the strata sizes prior to conducting the exploratory analyses. Interaction terms (e.g. age with behavioral interventions, sex with behavioral interventions, etc.) will be utilized to determine if specific groups respond well to specific intervention elements. Baseline BP may also play an important role. We will examine its impact by dividing the cohort into tertiles. We will repeat the above primary and exploratory modeling within each of the three initial BP strata to determine if there is heterogeneity of effect (e.g. do patients with the highest baseline BPs get the most benefit from the intervention components?). We will similarly assess the impact of the intervention components on the exploratory and process outcomes using linear, Poisson, logistic, or ordinal regression depending on the distributions. In addition, we will conduct longitudinal analyses that include all BP measurements over time (including those by text and at the in-person visits) to assess the temporal profiles of response in the intervention components.

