9.3 Sample Size and Accrual

We originally planned to enroll approximately 960 patients into the eligibility phase. From this group, we estimate that 480 participants will report qualifying BPs and will be randomized to one of the eight intervention arms. We anticipate 240 participants will fully complete the 12 month, in person follow up visits.

However, after accruing approximately 400 randomized participants, we noted lower than expected retention at 6 month visits. Therefore, we will adjust the maximum total number of enrollments and randomizations upwards by 50% each. The overall intention is to achieve approximately 240 protocol completers (attendees at 12-month visit). We will continue to monitor accrual and retention in order to achieve this target.

In the work by Collins and others, methods for sample size estimations for factorial design, MOST based interventions, have previously been reported. It is important to note, that the primary hypotheses driven by these designs is not in the pairwise comparisons of each of the interventions, but instead is the overall estimate of the effects of each of the individual intervention components, and their combinations. This smallest standardized effect size of 0.35 corresponds to a BP change of 1 mm Hg and standard deviation of 2.8 mm Hg for each parameter. We believe this is the minimal clinically significant change for each component; and to achieve improvements of 3-4 mm Hg over the course of a year, our chosen regimen for the next phase

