Analysis Plan: The primary analysis (aim 1) will fit a linear regression model with the outcome of SBP change (baseline minus 12 months) and main effect-coded binary predictors of healthy behavior texts (yes vs. no), prompted BP self-monitoring frequency (high vs. low), and primary care provider visit scheduling and transportation (active vs. passive). Initial analyses will focus on the main effects. Additional analyses will include all the two-way interactions of the three intervention components (only considering interactions where at least one of the factors in the interaction demonstrates a sufficiently large main effect). As the goal of this exploratory trial is to find interventions and combinations with activity, we will use an alpha level of 0.10 for all main effects and 0.20 for interactions. We plan to include elements meeting that bar for statistical significance in the subsequent multicenter trial. If significant interactions exist (i.e. the combination of facilitated transportation and high frequency home BP monitoring), we plan to implement the combination of elements that has the highest expected reduction in SBP – assuming we achieve significance at the p=0.1 (main effects) or 0.2 (interaction) level for the components. In the event of an overall “null” trial, we would examine the expected change in SBP for arm 1, which would be represented by the intercept. If this was significantly greater than 0 at the p=0.1 level we would propose a very simple subsequent multi-center trial using only weekly prompted BP self-monitoring.

The main secondary analyses (aim 2) will use time-to event (Cox Proportional Hazards) and logistic regression. For the endpoint of interest, (either time to first primary care visit, or the binary variable indicating attendance at two or more primary care visits within 1 year of randomization), we will fit an adjusted regression model. The main predictor of interest for these models is assignment to the active primary care provider scheduling and transportation arm (50% of all subjects randomized in the trial), while adjusting for the assignment into other groups similar to aim 1 (healthy behavior text messages and prompted BP self-monitoring).

2. Analysis Plan

2.1 Preliminary evaluation of data:

Purpose: To identify issues that will affect our approach to the primary analysis. Specifically:

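### The primary model for SBP change has no baseline SBP term, so it fixes the baseline slope at 1 and gives up some precision

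*SAP*

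**What the plan says.** SAP 2.4 defines the outcome as baseline SBP (the median of three eligibility-phase readings) minus 12-month SBP and states: "The primary analysis will fit a linear regression model with the outcome of SBP change and main effect-coded binary predictors". The equation runs from β0 to β7. It contains the three components as 0/1 indicators, then female, age 65 or over, antihypertensive use and Black. Baseline SBP is not on the right-hand side and is not a randomisation stratum.

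Protocol 9.1 says "Baseline BP may also play an important role", and follows this with tertile analyses for heterogeneity of effect, which SAP 2.6 repeats. Elsewhere baseline BP appears in the baseline table (SAP 2.3). The secondary longitudinal model (SAP 2.5a) has a random intercept.

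Three other statements concern the same model:

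- SAP 2.4: "The outcome will be transformed (e.g., log) if necessary".
- SAP section 1, on what follows a null trial: "we would examine the expected change in SBP for arm 1, which would be represented by the intercept". Protocol 9.1 has the same rule.
- Protocol 9.1: "The primary analysis (aim 1) will fit a linear regression model with the outcome of SBP change (baseline minus 12 months"; the predictors listed there, and in SAP section 1, are the three components only. Protocol 9.1 then says: "We will conduct additional exploratory analyses using the stratification factors (age, sex, and antihypertensive use) as covariates". SAP 2.4 puts those factors, and race, in the primary model.

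**The concern.** Moving baseline SBP to the right-hand side turns the SAP 2.4 equation into 12-month SBP = 1 × baseline SBP − (linear predictor). The slope on baseline is therefore set at 1 and not estimated. Protocol 5.3.4 randomises only people who text in at least one raised reading, and selection of that kind invites regression to the mean, so a slope below 1 is likely.

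If the slope is below 1, subtracting the whole baseline corrects too much for chance imbalance. A component whose participants happen to start higher shows a larger reduction than it earned. The trial exists to choose components for a later study, through main-effect tests at 0.10 and interaction tests at 0.20, and those tests would be less precise than the collected data allow.

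The linked wording has its own consequences. The null-trial rule would test a reference stratum instead of arm 1, and two different primary models are on file.

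**Working it through.** **Inputs from the documents.** Effect and SD from protocol 9.3: "corresponds to a BP change of 1 mm Hg and standard deviation of 2.8 mm Hg for each parameter". Alpha is 0.10, two-sided. The required number is 196, with 240 completers expected. Each factor is taken as 1:1. The hoped-for improvement is also from protocol 9.3: "to achieve improvements of 3-4 mm Hg over the course of a year".

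**Inputs assumed.** The documents do not give the baseline-to-12-month correlation ρ, the ratio k of 12-month SD to baseline SD, or whether 2.8 is the SD of change. I take 2.8 as the SD of change and add 15 mm Hg as a second case.

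**1. The plan's own figure.** For a 1:1 factor, SE = 2 × SD / √N. With d = 1/2.8 = 0.357, the noncentral t with seven model terms gives power 0.801 at N = 196, which reproduces the plan. At N = 240 it gives 0.867.

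**2. Variance ratio, adjusted to change score.** Ratio = k²(1 − ρ²) / (1 + k² − 2ρk), which is (1 + ρ)/2 when k = 1. The slope is kρ. Power is for 1 mm Hg at SD of change 2.8 and N = 240, with SE = 2 × 2.8 × √(ratio/240).

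| k | ρ = 0.3 | ρ = 0.5 | ρ = 0.7 | Power |
|---|---|---|---|---|
| 1 | 0.65 | 0.75 | 0.85 | 0.96, 0.94, 0.91 |
| 1.25 | 0.78 | 0.89 | 0.98 | 0.93, 0.90, 0.87 |
| 1.5 | 0.87 | 0.96 | 1.00 | 0.905, 0.88, 0.87 |

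**3. Ratio under the plan's eligibility rule.** This simulation assumed true SBP with mean 135 or 145, between-person SD 12 or 15 and within-person SD 8 or 12. Three readings were drawn, entry required any SBP of 140 or more (the diastolic route was ignored), baseline was the median of three, and the 12-month value was one reading.

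- True SBP stable over the year: ratio 0.91 to 0.97, slope 0.61 to 0.86.
- True SBP correlated 0.6 over the year: ratio 0.82 to 0.88, slope 0.37 to 0.51.
- The 12-month SD came out at 1.15 to 1.45 times the baseline SD, so the equal-SD row above is the favourable end.
- Effective completers: 240/0.97 = 247 and 240/0.82 = 293. The best equal-SD case is 240/0.65 = 369.

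**4. If the SD of change is 15.** SE = 2 × 15/√240 = 1.94. Power for 1 mm Hg is 0.145, and 0.159 with ratio 0.75. The effect detectable at 80% power is 2.487 × SE: 4.8 mm Hg unadjusted and 4.2 mm Hg adjusted (SE 1.68).

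**5. Chance imbalance carried into a main effect.** The imbalance has SD 2 × s_baseline/√240, and the carried part is (1 − kρ) times that. With k = 1 and ρ = 0.5, the baseline SD equals the SD of change.

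- SD 2.8: 0.36 × 0.5 = 0.18 mm Hg.
- SD 15: 1.94 × 0.5 = 0.97 mm Hg. Keeping SD of change 15 and ρ = 0.5, it falls to 0.76, 0.63 and 0.41 at k = 1.15, 1.25 and 1.45.

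A trial simulation (N = 240, three factors, true effect 1, equal SDs of 15, 3,000 runs) agreed. At ρ = 0.3, 0.5 and 0.7 the change-score estimate moved 0.72, 0.50 and 0.29 mm Hg per mm Hg of imbalance, and the adjusted estimate about 0. Mean estimates were 0.96 to 1.05 in both models.

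**6. Log transform.** The log of a change is undefined at zero or below. Under a normal distribution, P(change ≤ 0) = Φ(−mean/SD). At SD 2.8 this is 0.142 for a mean of 3 and 0.077 for a mean of 4. At SD 15 it is 0.421 and 0.395.

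**7. Intercept.** Setting every SAP 2.4 indicator to 0 gives arm 1 for men under 65, without antihypertensives in the past 6 months, and not Black. That equals the arm 1 mean only if β4 to β7 contribute nothing on average. The rule fits the three-factor model of SAP section 1 with 0/1 coding, but not the model of SAP 2.4.

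**The case against.** The strongest reply is that this is an efficiency choice and not an error. That stands: the change score is unbiased over randomisations, type I error is unaffected, and 240 completers already give 0.867 power on the plan's inputs.

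It can also be said that lost precision and carried imbalance are one harm counted twice. That is right. Var(change) − Var(adjusted residual) = (1 − b)² × Var(baseline), where b is the slope, so the unadjusted standard error already contains the imbalance. The (1 − slope) statement describes one realised trial and is not an additional bias.

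The equal-SD figures are the favourable end, and at k = 1.5 with ρ = 0.7 the slope is 1.05, so the direction reverses slightly. The eligibility-based range should lead, and its lower end is a gain of about 3%. The figures also price 240 complete cases, while SAP 2.4 plans multiple imputation over all randomised participants; the gain under that analysis has not been worked out.

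The protocol's remark on baseline BP introduces tertile analyses and does not admit to a missing covariate. That is a fair reading. But tertile models address heterogeneity, and the random intercept belongs to a separate longitudinal model. Neither is a baseline-adjusted primary estimate.

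Finally, the log, intercept and covariate-list points are not caused by the omission. They are corrections to the same model and stand on their own.

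**Conclusion.** The concern holds as a recommended change. The omission and the fixed slope can be read directly from SAP 2.4. The likely gain from adjustment is modest: a variance ratio of 0.82 to 0.97 under the simulated eligibility rule, and 0.65 in the best equal-SD case. On the plan's inputs, power rises from 0.867 to at most 0.96. With an SD of change of 15 mm Hg, power for 1 mm Hg stays near 0.15, so adjustment does not repair the sample size. All these sizes rest on assumed correlations and SDs, so confidence in the magnitude is medium. The intercept fault and the conflict between covariate lists depend on no assumed correlation and need correcting in any case.

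**What to change.** - Add continuous baseline SBP, centred at its mean, to the SAP 2.4 equation, and use that model for the interaction tests. Keeping change as the outcome or switching to 12-month SBP gives the same component effects apart from sign.
- State the same model and covariates in protocol 9.1 and SAP section 1.
- Replace the example log of change with robust standard errors, or with log 12-month SBP and log baseline SBP as covariate.
- In the null-trial rule, replace the intercept with the model-based mean change for arm 1, averaged over the observed covariates.
- If results are already known, report the baseline-adjusted model as a labelled post-hoc analysis under SAP section 3.

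The cost is wording in the two documents and one degree of freedom. No new data are needed.
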